# NON-INTERVENTIONAL (NI) STUDY PROTOCOL

### **PASS** information

Title	An Active Surveillance Study to Monitor the Real-World		
	Safety of Ritlecitinib Among Patients with Alopecia Areata		
	in Denmark, France, and Sweden		
Protocol number	B7981101		
Protocol version identifier	1.0		
Date	01 March 2024		
EU Post Authorization	To be registered before the start of data collection		
Study (PAS) register			
number	D (1, 1), 1		
Active substance	Riflecitinib		
	ATC code L04AF08		
Medicinal product	Littulo		
Product reference	EU/1/23/1755/001. EU/1/23/1755/002. EU/1/23/1755/003		
Procedure number	EMEA/H/C/006025		
Marketing Authorization	Pfizer Europe MA EEIG		
Holders	[name]		
	[name]		
	Belgium		
Joint PASS	No		
Research question and	Research question: What are the incidence rates (IRs) of		
objectives	the safety events of interest among patients with alopecia		
	areata (AA) receiving ritlecitinib and patients with AA		
	receiving other approved systemic treatments for AA in a		
	real-world setting?		
	Primary objective: to estimate the IRs of safety events of		
	interest among patients with AA initiating ritlecitinib and		
	patients with AA initiating baricitinib or other approved		
	systemic treatments for AA in a real-world setting. The		
	following are the primary safety events of interest:		

Staff must always refer to and follow the current official electronic document repository version. This document was created based on QMS04-GSOP-SD-GL06 9.0 CMCD Forms Template WORD 01-Nov-2021 Page 1 of 47

	• Thromboembolic events (including venous thromboembolism [VTE] and arterial thrombosis)	
	Herpes zoster	
	Serious infections	
	Opportunistic infections	
	Malignancy	
	
 
Malignancy excluding nonmelanoma skin cancer (NMSC)
 
	
	• NMSC	
	• Major adverse cardiovascular events (MACE)	
	Neurological events of interest	
	• Peripheral neuropathy	
	
 
Sensorineural hearing loss
 
	
	
 
Migraine
 
	
	
 
Seizures and seizure disorders
 
	
	
 
Demyelinating disorders including multiple sclerosis
 
	
	
 
Neurodegenerative disorders
 
	
	Bone fractures	
	• Growth metrics in adolescents (Denmark only)	
	Exploratory objective: to compare incidence rates of the safety events of interest among patients with AA initiating ritlecitinib and patients with AA initiating baricitinib or other approved systemic treatments for AA, if study size permits.	

# 2. LIST OF ABBREVIATIONS

Abbreviation	Definition		
AA	alopecia areata		
AE	adverse event		
ALS	amyotrophic lateral sclerosis		
AT	alopecia totalis		
ATC	Anatomical Therapeutic Chemical		
ATE	arterial thromboembolism		
AU	alopecia universalis		
CCAM	Classification commune des actes médicaux		
CCI	Charlson Comorbidity Index		
CepiDC	French National Death Register		
CESREES	Comité Ethique et Scientifique pour les Recherches, les Etudes et les		
	Evaluations dans le domaine de la Santé		
CHMP	Committee for Medicinal Products for Human Use		
CI(s)	confidence interval(s)		
CIOMS	Council for International Organizations of Medical Sciences		
CIP	Code Identifiant de Présentation		
COVID-19	coronavirus disease of 2019		
CNIL	Commission Nationale de l'Informatique et des Libertés		
CPR	Central Personal Registration		
CV	cardiovascular		
CVD	cardiovascular disease		
DLQI	Dermatology Life Quality Index		
DVT	deep vein thrombosis		
EMA	European Medicines Agency		
ENCePP	European Network of Centres for Pharmacoepidemiology and		
	Pharmacovigilance		
EU	European Union		
FDA	Food and Drug Administration		
GPP	Good Pharmacoepidemiology Practices		
GVP	Good Pharmacovigilance Practices		
HIV	human immunodeficiency virus		
HR	hazard ratio		
HZ	Herpes zoster		
IBD	inflammatory bowel disease		
ICD	International Statistical Classification of Diseases		
ICD-10	International Classification of Disease, 10th Revision		
ICD-11	International Classification of Disease, 11th Revision		
IQR	interquartile range		
IEA	International Epidemiological Association		
IEC(s)	Independent Ethics Committee(s)		
IPTW	inverse-probability treatment weighting		

PFIZER CONFIDENTIAL

CT24-WI-GL02-RF02 5.0 Non-Interventional Study Protocol Template For Secondary Data Collection Study 01-Aug-2023 Page 6 of 47

Abbreviation	Definition
IR(s)	incidence rate(s)
IRB(s)	Institutional Review Board(s)
ISPE	International Society for Pharmacoepidemiology
ITT	Intention-to-treat
JAK	Janus kinase
MACE	major adverse cardiovascular event
MAH	Marketing Authorization Holder
MI	myocardial infarction
NI	non-interventional
NIS	non-interventional study
NMSC	nonmelanoma skin cancer
NOMESCO	Nordic Medico-Statistical Committee
NSAIDs	non-steroidal anti-inflammatory agents
PAS	Post-authorization study
PASS	Post-authorization safety study
PE	pulmonary embolism
PRAC	Pharmacovigilance Risk Assessment Committee
PY(s)	person-year(s)
SALT	Severity of Alopecia Tool
SAP	Statistical Analysis Plan
SMA	spinal muscular atrophy
SNDS	Système National des Données de Santé
UCD	Unité Commune de Dispensation
US	United States
VTE	venous thromboembolism
WHO	World Health Organization

### 4. ABSTRACT

**Title** An Active Surveillance Study to Monitor the Real-World Safety of Ritlecitinib Among Patients with Alopecia Areata in Denmark, France, and Sweden

Protocol B7981101; Version 1.0; 01 March 2024

Main author: [name], Aarhus University

**Rationale and background** Alopecia Areata (AA) is an autoimmune disease that has an underlying immuno-inflammatory pathogenesis and is characterized by nonscarring hair loss ranging from small patches to complete scalp, face, and/or body hair loss. Ritlecitinib is an orally administered Janus kinase 3 (JAK3) and TEC family kinase inhibitor. Ritlecitinib was authorized by the European Medicines Agency (EMA), on 15 September 2023, "for the treatment of severe alopecia areata in adults and adolescents 12 years of age and older". This non-interventional (NI) study is designated as a post-authorization safety study (PASS) and is a commitment to the European Medicines Agency (EMA).

### **Research question and objectives**

Research question: what are the incidence rates (IRs) of the safety events of interest among patients with AA initiating ritlecitinib and patients with AA initiating baricitinib or other approved systemic treatments for AA in a real-world setting?

Primary objective: to estimate the incidence IRs of safety events of interest among patients with AA initiating ritlecitinib and patients with AA initiating baricitinib or other approved systemic treatments for AA in a real-world setting.

Exploratory objective: to compare the rates of the safety events of interest among patients with AA initiating ritlecitinib and patients with AA initiating baricitinib or other approved systemic treatments for AA, if study size permits.

Study design Cohort study using routinely collected population-based data.

**Population** The study population will include patients with AA initiating ritlecitinib, baricitinib or another approved systemic AA treatment as recorded in the participating data sources in Denmark, France, and Sweden during the cohort accrual period. Patients will be included between 15 September 2023 until 14 September 2031 and followed through 14 September 2033.

**Variables** The safety events of interest are thromboembolic events (including VTE and arterial thrombosis); herpes zoster; serious infections; opportunistic infections; malignancy (including malignancy excluding nonmelanoma skin cancer (NMSC) and NMSC); major adverse cardiovascular events (MACE); neurological events of interest (including peripheral neuropathy, sensorineural hearing loss, migraine, seizures and seizure disorders, demyelinating disorders including multiple sclerosis, and neurodegenerative disorders); bone fractures; and growth metrics in adolescents (Denmark only). In addition, measured

PFIZER CONFIDENTIAL

CT24-WI-GL02-RF02 5.0 Non-Interventional Study Protocol Template For Secondary Data Collection Study 01-Aug-2023

demographic and clinical characteristics (as available in the available routinely collected data) will be described and used in the analysis, including age, sex, and selected comedications and co-morbidities.

**Data sources** This study, based on secondary data, will use routinely collected data from population-based registers in Denmark and Sweden, and an administrative healthcare database in France. All participating countries have universal healthcare.

**Study size** All eligible patients initiating ritlecitinib or comparator treatment during the first 8 years following ritlecitinib approval in the 3 countries will be included.

**Data analysis** Distributions of the characteristics of patients with AA will be reported separately for ritlecitinib and comparator groups at treatment start, using appropriate summary statistics. IRs and cumulative incidences of the safety events of interest will be computed (primary objectives) and the risks will be compared, if study size permits (exploratory objectives), between initiators of ritlecitinib and initiators of comparator AA treatments. If conducted, measured confounding in the comparative analysis will be controlled using a propensity-score based method; unmeasured confounding will be quantified using the E-value method.

**Milestones** Data collection will start in September 2027 and end in September 2035. Start of data collection is defined as the date on which the data extraction starts for the first interim report. End of data collection is defined as the date from which the analytical dataset is completely available for the final study report. The analytical dataset is the dataset that contains clean and coded data from all participating countries/databases. Four interim reports will be generated in September 2028, 2030, 2032, and 2034 followed by the final report in March 2036.

### **5. AMENDMENTS AND UPDATES**

None.

### 6. MILESTONES

Milestone	Planned date a	Comments
Registration in the EU	August 2027	Prior to initiating data collection.
PAS register	-	
Draft protocol submission	March 2024	Within 6 months from approval of ritlecitinib in
		the European Union (EU).
Start of data collection b	September 2027	Within 4 years from approval of ritlecitinib in
		the EU.
End of data collection c	September 2035	Within 2 years after the end of study period,
		considering the lag in data availability in the
		respective data sources.
Interim analysis reports d	September 2028	The 1st interim report is planned to be
	September 2030	submitted within 5 years of approval of
	September 2032	ritlecitinib in the EU, considering the lag in data
	September 2034	availability in the respective data sources.
		Subsequent interim reports are planned every 2
		years thereafter over 6 years (4 interim reports
		total).
Final study report d	March 2036	Final study report is planned for submission
		within 6 months from the end of data collection.

a EU approval 15 September 2023.

b Defined as the date from which data extraction starts for the first interim report.

c Defined as the date from which the analytical dataset is completely available for the final study report. The analytical dataset is the dataset that contains clean and coded data from all participating countries/databases.

d Interim reports will contain analyses addressing the primary objectives. The final study report will be inclusive of all objectives, conditional on feasibility of the exploratory objective

### 7. RATIONALE AND BACKGROUND

Alopecia Areata (AA) is an autoimmune disease with immuno-inflammatory pathogenesis characterized by nonscarring hair loss. AA may present as: limited patchy hair loss (patchy alopecia areata), complete loss of hair on the scalp (alopecia totalis [AT]), or complete loss of hair on the scalp and the body (alopecia universalis [AU]). Other clinical variants of AA, such as ophiasis alopecia or diffuse AA, have also been described (1). The affected skin usually does not have signs of inflammation.

AA is the second most common cause of hair loss, affecting approximately 147 million individuals of both sexes and all ethnicities worldwide (2, 3). Incidence rates of AA range from 20 to 200 per 100,000 person-years, and the global lifetime prevalence is estimated at 2% (3-9). A meta-analysis of evidence published up to 1 September 2018 estimated the overall pooled incidence proportion of AA in Europe as 4.92% (95% confidence interval [CI] 2.41-8.25%) and the pooled prevalence as 0.58% (95% CI 0.49-0.66%) (10). AA is associated with inflammatory diseases including asthma, allergic rhinitis, atopic dermatitis, and with autoimmune diseases such as thyroiditis and vitiligo (1). The natural history, clinical course and prognosis of AA are unpredictable and can be marked by remission, progression, or persistence (11, 12).

Ritlecitinib is an orally administered Janus kinase (JAK) 3 and TEC family kinase inhibitor. Ritlecitinib was authorized by the European Medicines Agency (EMA), on 15 September 2023, for the treatment of severe alopecia areata in adults and adolescents 12 years of age and older (13). Ritlecitinib is dispensed by prescription only, and in Denmark, currently only in hospital settings. Ritlecitinib is flagged by the Danish authorities as a medication being subject to heightened monitoring (14).

Baricitinib is the only other systemic therapy approved for AA (approved in June 2022). Baricitinib's other indications in the EU are moderate to severe active rheumatoid arthritis in adult patients who have responded inadequately to, or who are intolerant to one or more disease modifying anti rheumatic drugs; moderate to severe atopic dermatitis in adult and paediatric patients 2 years of age and older who are candidates for systemic therapy; and active juvenile idiopathic arthritis in patients 2 years of age and older who have had an inadequate response or intolerance to one or more specific prior conventional synthetic or biologic disease modifying anti rheumatic drugs (15).

According to the treatment guidelines of the Danish Dermatological Society, updated in July 2023, systemic treatment for AA can be considered in patients meeting all of the following criteria: (1) established AA diagnosis; (2) disease duration >6 months without new lesions, but <8 years if a new lesion has been observed within an 8-year period; (3) severe AA, corresponding to hair loss covering more than 50% of the scalp as measured with the Severity of Alopecia Tool (SALT) score; and (4) Dermatology Life Quality Index (DLQI)  $\geq$ 10. The 2023 guidelines cite baricitinib, 4 mg daily, as the best documented treatment, following the necessary workup and observing the label restrictions. Baricitinib is indicated for adults, with special caution in patients 65 years of age or older, patients at increased risk of serious cardiovascular disease, patients with a history of smoking and patients at an increased risk of cancer or venous thromboembolism (VTE). The above guidelines require that the effect of systemic treatment be continuously assessed at 3, 6, 9 and 12 months, and

PFIZER CONFIDENTIAL

CT24-WI-GL02-RF02 5.0 Non-Interventional Study Protocol Template For Secondary Data Collection Study 01-Aug-2023

*O1-Aug-2023* Page 12 of 47

that the treatment be discontinued if both of the following efficacy targets are not achieved after 36 weeks of treatment: (1) SALT score <20% and (2) DLQI <5 (16). However, as of 24 January 2024, the Danish Medical Council (Medicinrådet) no longer recommends baricitinib treatment for severe AA. The Council recommends systemic treatment with combination of methotrexate and prednisolone as the best documented treatment, recommended for patients with long-term widespread disease following a thorough workup (17).

The Swedish Medical Products Agency's guideline on medical treatment of AA, last modified on 06 February 2024, currently cites absence of an effective treatment for AA, however, the guideline is pending an update in early 2024 (18). In France, as of 25 October 2023, baricitinib is the first-line treatment for severe adult alopecia (scalp involvement  $\geq$  50%), with the importance of monitoring various biological parameters (including haematological and lipid levels) and the contraindication in pregnancy. In accordance with the conclusions of the Pharmacovigilance Risk Assessment Committee (PRAC), patients ages 65 years and older, patients with a history of atherosclerotic cardiovascular disease or other cardiovascular risk factors (long-term or former smokers), and patients with risk factors for malignant tumours are advised that baricitinib should only be used in the absence of appropriate therapeutic alternatives. The benefit/risk balance of treatment should be reassessed at regular intervals. Discontinuation of treatment should be considered in patients who show no therapeutic benefit after 36 weeks of treatment (19).

Safety surveillance studies using electronic healthcare databases have been used to successfully monitor real-world safety of newly approved products across a wide spectrum of therapeutic areas and safety events. As part of the ritlecitinib pharmacovigilance plan, this non-interventional study (NIS) based on routinely collected electronic healthcare data from routine clinical practice will be conducted to actively monitor the safety events of interest following exposure to ritlecitinib, baricitinib or other approved systemic treatments for AA following the EU approval of ritlecitinib.

This NIS is designated as a post-authorization safety study (PASS) and is a commitment to the EMA.

### 8. RESEARCH QUESTION AND OBJECTIVES

### 8.1. Research Question

The research question is: What are the IRs of the safety events of interest among patients with AA initiating ritlecitinib and patients with AA initiating baricitinib or other approved systemic treatments for AA in a real-world setting?

# 8.2. Primary Objective

The primary objective is to estimate the IRs of safety events of interest among patients with AA initiating ritlecitinib and patients with AA initiating baricitinib or other approved systemic treatments for AA in a real-world setting. The following are the primary safety events of interest:

- Thromboembolic events (including VTE and arterial thrombosis)
- Herpes zoster (HZ)
- Serious infections
- Opportunistic infections
- Malignancy
  - Malignancy excluding nonmelanoma skin cancer (NMSC)
  - o NMSC
- Major cardiovascular event (MACE)
- Neurological events of interest
  - Peripheral neuropathy
  - Sensorineural hearing loss
  - o Migraine
  - o Seizures and seizure disorders
  - o Demyelinating disorders including multiple sclerosis
  - o Neurodegenerative disorders
- Bone fractures
- Growth metrics in adolescents (height and weight, conditional on sufficient data available beyond age 12 years; Denmark only)

# 8.3. Exploratory Objective

The exploratory objective is to compare the IRs of the safety events of interest among patients with AA receiving ritlecitinib and patients with AA receiving baricitinib or other approved systemic treatments for AA, if study size permits. The decision rule for whether the

PFIZER CONFIDENTIAL

CT24-WI-GL02-RF02 5.0 Non-Interventional Study Protocol Template For Secondary Data Collection Study 01-Aug-2023 Page 14 of 47 comparative analysis can be conducted will be based on the expected number of users and observed number of events and will be specified in the Statistical Analysis Plan (SAP).

### 9. RESEARCH METHODS

### 9.1. Study Design

This will be a cohort study based on routinely and prospectively collected electronic healthcare data in Denmark, France, and Sweden. The study population will include a cohort of patients with AA initiating ritlecitinib and, to contextualize the results, cohorts of patients with AA initiating baricitinib or other systemic AA treatments (if approved for the same indication in the EU).

# 9.1.1. Study Population and Study Period

The study population will include eligible patients (described in Section 9.2) with AA initiating ritlecitinib, baricitinib or other approved systemic AA treatments during the cohort accrual period. The cohort accrual period will include the first 8 years following ritlecitinib approval (15 September 2023 to 14 September 2031). The study period will include follow-up through 14 September 2033, to allow a minimum of 2 years of follow-up for the last patient accrued, given some longer-latency outcomes.

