### 9.5. Study Size

All ritlecitinib-treated patients meeting study inclusion and exclusion criteria in all data sources during the accrual period will be included in the study. Estimated anticipated group size of the ritlecitinib-exposed population across the three databases is provided in Table 2. Overall, an estimated 835 ritlecitinib-exposed patients are expected to be accrued over 8 years. Of note, these sample size calculations are estimates based on the projected uptake of ritlecitinib in the study countries and are subject to the actual uptake and final study inclusion and exclusion criteria.

			Y	ears Post-	-Approval			
	Year 1	Year 2	Year 3	Year 4	Year 5	Year 6	Year 7	Year 8
Estimated New Patients Treated Per Year in Denmark, France, and Sweden (based on projected market uptake)	0	148	192	220	255	288	321	247
Estimated 50% Meeting Eligibility Criteria (conservative estimate, true proportion may be higher)	0	74	96	110	127	144	161	123
Estimated Cumulative Number of Patients Exposed to Ritlecitinib	0	74	170	280	407	551	712	835

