With an estimated 835 ritlecitinib-exposed patients accrued over 8 years (Table 2), and with a 10-year study period, the expected number of observed PYs will be 0\*9 + 74\*8 + 96\*7 + 110\*6 + 127\*5 + 144\*4 + 161\*3 + 123\*2 = 3,864, assuming no lost to follow-up. A 1:1 ratio of ritlecitinib:comparator patients would yield a total of 7,728 PYs and an expected number of events of 9, 10, and 15 for the endpoints malignancy, thromboembolic events, and serious infections during follow-up. In this setting, there would be sufficient power to detect a minimum HR of 6.7, 6.4, and 4.3 for the endpoints malignancy, thromboembolic events, and serious infections (or other outcomes of similar incidence). However, the analysis will be conducted separately by data source and each individual data source is unlikely to accrue 835 ritlecitinib-exposed patients.

Minimum detectable HRs will be lower for the subgroup analysis of patients with a minimum of 5 years of follow-up (during the 10-year study period). 407 ritlecitinib-exposed patients

PFIZER CONFIDENTIAL

CT24-WI-GL02-RF02 5.0 Non-Interventional Study Protocol Template For Secondary Data Collection Study 01-Aug-2023 Page 28 of 47 accrued over 5 years (Table 2), assuming a 1:1 ratio and no lost to follow-up, would provide sufficient power to detect minimum HRs of 10.3, 9.9, and 6.1 for the endpoints malignancy, thromboembolic events, and serious infections.

Of note, it is possible that the comparator groups may be larger than the ritlecitinib group, given baricitinib's earlier approval date and the potential inclusion of other EU approved systemic treatments. If patients are receiving baricitinib at a substantially higher rate than ritlecitinib (e.g., a ratio of 2:1 or greater), then the minimum detectable hazard ratios could be met with fewer ritlecitinib-exposed patients.

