### 9.7.3. Analyses of the Exploratory Objective

An exploratory comparative analysis estimating hazard ratios of the safety events of interest among AA patients treated with ritlecitinib compared with patients treated with baricitinib or other systemic treatment will be conducted for the final report only, study size permitting. This analysis will use Cox's proportional-hazards regression to estimate HRs and 95% CIs. To account for potential confounding in the comparative analysis, a propensity-score based method, such as inverse-probability treatment weighting (IPTW) will be used to balance measured characteristics of the exposure cohorts being compared (51). The covariate balance between the exposure cohorts (before and after IPTW) will be evaluated using standardized differences for continuous covariates and standardized differences of proportion for each (non-missing) category for categorical covariates. Characteristics with standardized differences greater than 0.10 after weighting will indicate imbalance and will be adjusted for in the comparative analyses. If IPTW is applied, robust variance estimators will be used to address lack of independence between patients induced by weighting. The extent of unmeasured confounding will be assessed using the E-value method (52, 53). Full details of the methods will be provided in the SAP.

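### The exploratory hazard ratios are not restricted to concurrent initiators, although accrual opens for all cohorts in a year when the plan projects no ritlecitinib starters

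*Protocol*

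**What the plan says.** Section 9.1.1 defines the population as patients "initiating ritlecitinib, baricitinib or other approved systemic AA treatments during the cohort accrual period" and sets that period once for all of them: "The cohort accrual period will include the first 8 years following ritlecitinib approval (15 September 2023 to 14 September 2031".

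Section 9.5 projects ritlecitinib uptake by year since approval. In Table 2, both the row "Estimated New Patients Treated Per Year in Denmark, France, and Sweden (based on projected market uptake" and the row "Estimated 50% Meeting Eligibility Criteria (conservative estimate, true proportion may be higher" show 0 for Year 1. The person-year calculation carries the same zero: "the expected number of observed PYs will be 0\*9 + 74\*8 + 96\*7 + 110\*6".

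Section 7 gives baricitinib's approval for alopecia areata as June 2022, so its new users can enter from the first day of the window. The same section describes guidance that was moving during Year 1: "as of 24 January 2024, the Danish Medical Council (Medicinrådet) no longer recommends baricitinib treatment for severe AA", and the Swedish guideline was awaiting an update in early 2024.

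For the comparison, section 9.7.3 says that "a propensity-score based method, such as inverse-probability treatment weighting (IPTW) will be used to balance measured characteristics", with further adjustment for covariates whose standardized difference stays above 0.10. Calendar year of index date is a listed variable in section 9.3.3. Sections 9.2, 9.7.3, 9.7.4 and 9.7.5 contain no restriction to concurrent initiators. The 5-year subset in section 9.7.4 reuses 15 September 2023 as its opening date.

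**The concern.** A comparator who starts treatment before any ritlecitinib patient exists in that data source cannot be compared with a ritlecitinib patient from the same period. If such patients stay in the Cox model, changes over calendar time in prescribing, patient mix or coding can be read as differences between drugs. The guidance changes in section 7 make it plausible that the first year differs from later ones.

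Early starters also have the longest potential follow-up, so where follow-up is not cut at discontinuation their share of person-time exceeds their share of patients. This matters most for the 5-year subset, which is meant for outcomes with long induction or latency and draws only on the first five accrual years.

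Section 9.5 also treats baricitinib's earlier approval as a possible source of a larger comparator group and hence of smaller detectable hazard ratios. Part of that gain could come from patients with no counterpart.

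**Working it through.** **1. The plan's own figures.** The eligible ritlecitinib patients in Table 2 for Years 1 to 8 are 0, 74, 96, 110, 127, 144, 161, 123 (total 835). The multipliers in section 9.5 are 9, 8, 7, 6, 5, 4, 3, 2.

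- Person-years: 0×9 + 74×8 + 96×7 + 110×6 + 127×5 + 144×4 + 161×3 + 123×2 = 3,864; at 1:1, 7,728. Both match.
- Events at the Table 3 rates of 1.13, 1.17 and 1.89 per 1,000 person-years: 7,728 × rate / 1,000 = 8.73, 9.04 and 14.61. The plan states 9, 10 and 15, which are these values rounded up.
- Minimum detectable HR = exp[2(z0.975 + z0.80)/√events]. The protocol states neither alpha nor power; two-sided 0.05 and 80% are assumed. Results are 6.66, 6.45 and 4.33, against stated 6.7, 6.4 and 4.3.
- 5-year subset: 407 patients and 2,559 person-years per group give 10.28, 9.87 and 6.06, against stated 10.3, 9.9 and 6.1.

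The plan's figures reproduce. Ritlecitinib person-time from Year-1 starters is 0×9 = 0. The 1:1 calculation mirrors ritlecitinib accrual, so it contains no Year-1 comparator time either.

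**2. Year-1 share of the comparator.** The documents give no comparator uptake by year. The illustration assumes the same number of comparators each year and no discontinuation, with the plan's multipliers.

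| | Initiators | Person-years |
|---|---|---|
| Full window (multipliers sum to 44) | 1/8 = 12.5% | 9/44 = 20.5% |
| 5-year subset (9+8+7+6+5 = 35) | 1/5 = 20% | 9/35 = 25.7% |

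If follow-up per patient were the same whatever the start year, as it would tend to be when treatment is short and follow-up stops with it, the person-year shares would fall to the initiator shares.

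The uptake assumption matters more. Let a share s of 835 comparators start in Year 1 and the rest follow the ritlecitinib pattern. The Year-1 person-year share is then s×835×9 / [s×835×9 + (1−s)×3,864], which is 9% for s = 5%, 39% for s = 25% and 66% for s = 50%. The matching ritlecitinib share is 0% on the plan's projection.

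**3. What weighting does.** Let e be the probability of ritlecitinib given covariates.

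- Weights aimed at the whole population give a comparator 1/(1−e). With e = 0 that is 1, so the patient stays in with nobody on the other side to balance against.
- Weights aimed at the ritlecitinib-treated give e/(1−e). With e = 0 that is 0, so the patient drops out.

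Section 9.7.3 does not say which is meant. The listed covariate is calendar year, and 2024 spans both Year 1 (to 14 September 2024) and early Year 2. On the projection, only 15 September to 31 December 2023 is a stratum with no ritlecitinib at all.

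**4. Cost of dropping Year-1 comparators.** Minimum detectable HR = exp[(z0.975 + z0.80)/√(D·a·(1−a))], where D is total events at the background rate and a is the ritlecitinib share of person-years (3,864 fixed).

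| Comparators, level uptake | Comparator person-years | Minimum HR (malignancy, thromboembolic, serious infection) |
|---|---|---|
| 835, Year 1 kept | 835/8 × 44 = 4,592.5 | 6.17, 5.98, 4.08 |
| 835, Year 1 dropped | 835/8 × 35 = 3,653 | 6.84, 6.62, 4.42 |
| 1,670, Year 1 kept | 1,670/8 × 44 = 9,185 | 4.94, 4.81, 3.44 |
| 1,670, Year 1 dropped | 1,670/8 × 35 = 7,306 | 5.25, 5.10, 3.60 |

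The multipliers for Years 2 to 8 also sum to 35. That this equals the 5-year sum is a coincidence.

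**The case against.** The strongest reply is about scope. The hazard ratios are exploratory, for the final report only and conditional on study size. The primary objective is incidence rates by cohort, for which the full window is legitimate. Section 9.7 leaves method detail to the SAP, and restriction or trimming is often specified there. Accrual already starts at ritlecitinib's authorisation and not at baricitinib's earlier approval, and prior users of the same agent are washed out. All of this stands and limits the weight of the point. It does not remove it, because the protocol itself fixes the window and the 5-year subset and names no restriction for the comparison.

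Four stronger readings are tempting, and the documents do not support them:

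- A reader might infer that Year-1 baricitinib patients had no alternative on the market. Ritlecitinib was authorised on the first day of the window, and section 7 describes its dispensing as current. The Year-1 zero is a projection that section 9.5 makes subject to actual uptake.
- A reader might infer that Danish baricitinib starters will cluster before ritlecitinib arrives. Section 7 reports a change of recommendation and gives no counts before or after it.
- A reader might infer that weighting cannot solve the problem. That is true of weights for the whole population. Weights targeting the treated, or matching on a score that contains index period, would drop the empty stratum, and section 9.7.3 allows either.
- A reader might take the 20% and 26% person-year shares as expected values. They assume level uptake and no discontinuation, whereas Figure 1 censors at discontinuation or switch. Section 9.7.2 leaves approaches with and without that censoring open.

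**Conclusion.** The point holds for the exploratory hazard ratios, including those in the 5-year subset. One window serves all cohorts, the plan projects no ritlecitinib initiators in its first year, and nothing restricts the comparison to concurrent initiators. If the projection holds and whole-population weights are used, Year-1 comparators enter without a counterpart and the result rests on extrapolation across a period of changing guidance.

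The size is illustrative. Under level uptake it is 12.5% of comparator initiators and between 12.5% and 20.5% of person-years, depending on discontinuation; in the 5-year subset it is 20%, and between 20% and 25.7%. Other uptake patterns move these shares widely. If ritlecitinib is in fact dispensed early, the gap narrows. The primary incidence rates remain valid as descriptions, but reading them side by side carries the same calendar mismatch. The change is worth making because it is cheap and can be settled before extraction starts in September 2027.

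**What to change.** In section 9.7.3, and for the 5-year subset in section 9.7.4, restrict the hazard-ratio analyses in each country to comparators whose index date is on or after the first eligible ritlecitinib initiation in that data source. Include calendar period of index in the propensity score. Trim regions without overlap, or use weights that target the ritlecitinib-treated, because otherwise a single early dispensing would reopen a nearly empty period.

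Keep the full window for the descriptive incidence rates, and report the comparator rate for the concurrent window beside the full-window rate.

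The cost is a short addition to the text, a date filter and some comparator person-time in the exploratory analysis. With 835 comparators starting evenly, minimum detectable hazard ratios rise from about 6.2, 6.0 and 4.1 to 6.8, 6.6 and 4.4. On the plan's projection no ritlecitinib person-time is lost, and the stated 7,728 person-years and hazard ratios of 6.7, 6.4 and 4.3 do not change.
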